## 6.6 Unscheduled Visit

If a subject requires an additional visit during a study interval for their study hip, and is seen by one or more person listed on the Delegation of Authority Log, then the following information shall be repeated:

- Harris Hip Score
- Hip Evaluation
- HOOS Jr.
- Forgotten Joint Score
- Adverse Events (if applicable)

If a subject has an unscheduled visit after the 6 week interval (outside defined protocol window) for their study hip, with one or more person listed on the Delegation of Authority Log then the following information shall be collected:

- Harris Hip Score
- Hip Evaluation
- HOOS Jr.
- Forgotten Joint Score
- Adverse Events (if applicable)
- Radiographs
  - AP Femur
  - Lateral
- RSA Exam (supine position) if RSA Exam was not conducted in-window for previous visit.  
If subject is seen multiple times outside of the same defined protocol window, only one RSA Exam is required.

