## **9.12 Primary, Secondary, and Safety Endpoint Analyses**

### **9.12.1 Primary Endpoint Analysis**

#### RSA Measured Subsidence at 2 years

The primary endpoint of RSA measured subsidence (Y translation, also known as superior cup migration) results in the 2-year visit window will be summarized on the subset of subjects in the Per Protocol Analysis Set (primary analysis) who have 6 week and 2 year data for the analysis. The analysis will also be conducted on the subset of subjects in the Safety Analysis Set (supportive analysis) who have 6 week and 2 year data for the analysis. Standard continuous summaries will be provided along with 95% confidence intervals. These summaries will be provided for each surgical approach, as well as combined.

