### **9.12.2 Secondary Endpoint Analysis**

#### RSA Measured Subsidence at 3 months, 6 months and 1 year

The analysis for this secondary endpoint will be identical to the analyses described for the primary endpoint except conducted on the results in the 3 month, 6 month, and 1 year visit windows, respectively, using the Per Protocol Analysis Set and the Safety Set.

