## 2 Interval Windows

The study includes the following periods: Pre-op, Operative, Prior to Discharge, 6 Weeks, 3 Months, 6 Months, 1 Year, 2 Years. Intervals related to each are shown in Table 3, below.

Table 3 Interval Windows for Non-Radiographic Study Visits

Visit	Minimum Day	Maximum Day	Midpoint Day
Pre-Op*	-90	0	
Operative	0	0	0
Prior to Discharge	1	Discharge	
6 Weeks	28	56	42
3 Months	60	120	90
6 Months	135	225	180
1 Year	275	455	365
2 Years	640	820	730

\* For radiographs Pre-Op study film window is from -270 days to DOS.

Time point specific data collected to satisfy the primary and secondary efficacy-related objectives will be assessed for compliance with these intervals. Only data which can be attributed to the visit intervals in Table 3 will be used in the analysis of primary and secondary endpoints. This visit will be hereafter referred to as the Analysis Visit and the originally recorded visit as the Nominal Visit. If multiple measurements fall into the pre-

operative window, or into the ‘Prior to Discharge’ post-operative window, the result collected most proximate to surgery will be utilized. For all post-operative visits after the ‘Prior to Discharge’ visit, if multiple measurements fall into the window then the last value within the window will be utilized for analysis.

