## **6.6 Primary Endpoint and Associated Hypotheses**

### RSA Measured Subsidence at 2 years

The primary endpoint of RSA measured subsidence (Y translation from week 6 in mm, also known as superior cup migration) results in the 2-year visit window will be summarized on the subset of subjects in the Per Protocol Analysis Set (primary analysis) who have 6 week and 2 year data for the analysis. The analysis will also be conducted on the subset of subjects in the Safety Analysis Set (supportive analysis) who have 6 week and 2 year data for the analysis. Standard continuous summaries will be provided along with 95% confidence intervals. These summaries will be provided for each surgical approach, as well as combined.

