## **6.7 Secondary Endpoints**

### 6.7.1 RSA Measured Subsidence and maximal total point motion at 3 months, 6 months, 1 year, and 2 years

X, Y, and Z translations from week 6 in mm and A, Y, and Z rotations in degrees, and maximal total point motion in mm will be summarized at the 3 month, 6 month, 1 year, and 2 years visit windows using the Per Protocol Analysis Set and the Safety Set. Standard continuous summaries will be provided along with 95% confidence intervals. These summaries will be provided for each surgical approach, as well as combined.

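### Should RSA exams taken outside every visit window, some of them called for by Protocol 6.6, be given a planned supportive summary?

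*SAP*

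**What the plan says.** Protocol 6.6 covers the case "If a subject has an unscheduled visit after the 6 week interval (outside defined protocol window) for their study hip", provided delegated study staff see the subject. The items to collect then include "RSA Exam (supine position) if RSA Exam was not conducted in-window for previous visit".

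SAP 2 assigns data to visits by date. After setting out the windows it says "Only data which can be attributed to the visit intervals in Table 3 will be used in the analysis of primary and secondary endpoints", and it separates the date-based visit from the recorded one: "This visit will be hereafter referred to as the Analysis Visit and the originally recorded visit as the Nominal Visit". The endpoint sections follow this rule. SAP 6.6 and Protocol 9.12.1 summarise results in the 2-year window, in subjects "who have 6 week and 2 year data for the analysis". SAP 6.7.1 says the other RSA results "will be summarized at the 3 month, 6 month, 1 year, and 2 years visit windows", and Protocol 9.12.2 repeats the primary analysis "except conducted on the results in the 3 month, 6 month, and 1 year visit windows, respectively". The supportive Safety Set analysis carries the same data requirement as the Per Protocol one.

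SAP 6.11 rules out imputation, SAP 6.13 plans no sensitivity analyses, and SAP 6.14 leaves room for post-hoc work. SAP 3 describes all confidence intervals as exploratory. Protocol 12.3 gives an out-of-window visit as an example of a protocol deviation, and SAP 6.5 provides a listing of deviations.

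**The concern.** The protocol has the subject imaged, evidently to make up for a missed exam, and the SAP then sets the image aside if its date falls in no window. No planned table uses it. The Safety Set analysis cannot recover it, and only exploratory correlations or post-hoc work remain.

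The reference exam is the sensitive case. Every RSA migration value is a change from the 6-week exam (Protocol 6.7, SAP 6.1). A subject whose only reference falls on day 57 to 59 has no usable value at 3 months, 6 months, 1 year or 2 years, and the change in linear head penetration goes with it. A 2-year exam outside its window costs one time point, but that is the primary one. The study exists to set a benchmark for later products (Protocol 2.2), so one would want to know whether the excluded values differ from those kept.

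Two labels add to the unease. SAP Table 3 is titled as applying to non-radiographic visits although the RSA endpoints depend on it, and the Per Protocol definition in SAP 4 does not say whether an out-of-window exam qualifies a subject.

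**Working it through.** **Inputs.** Windows in days (Protocol Table 9-1, SAP Table 3): 28–56, 60–120, 135–225, 275–455, 640–820; 2-year midpoint 730. SD 0.2 mm and n = 30 per approach (SAP 5).

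**1. The plan's own figure.** 2 × SD/√n = 2 × 0.2/√30 = 0.0730 mm, which reproduces the stated 0.073 mm. With the t quantile on 29 degrees of freedom in place of 2, the margin is 0.0747 mm.

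**2. Days outside every window.** Days 57–59 (3), 121–134 (14), 226–274 (49) and 456–639 (184). The sum is 250 of the 764 days from day 57 to day 820 (32.7%), plus everything before day 28 and after day 820. This is a share of calendar days, not of exams: visits are planned around the window midpoints, so few should fall in the gaps.

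**3. Which exams can lower the primary n.** The primary analysis needs an in-window reference and an in-window 2-year exam.
- Reference side: an exam on days 57–59, and also one before day 28.
- 2-year side: an exam after day 820, and also an early one. A nominal 2-year exam on day 639 with no later exam is lost exactly as one on day 821 is.
- A make-up exam for 3 months, 6 months or 1 year that falls in a gap does not affect the primary n.
- A subject with no 6-week exam whose first exam falls on days 60–120 is in window for 3 months but has no reference, so no 6-week-referenced value exists. Admitting out-of-window exams does not help this subject.

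**4. Loss of precision (counts are assumptions; the documents give none).**

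| Lost of 30 | n | 2 × 0.2/√n (mm) | Change |
|---|---|---|---|
| 0 | 30 | 0.0730 | – |
| 1 | 29 | 0.0743 | +1.7% |
| 3 | 27 | 0.0770 | +5.4% |
| 6 | 24 | 0.0816 | +11.8% |

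Losing one subject (0.0743 mm) moves the margin less than the plan's use of 2 in place of the t quantile (0.0747 mm).

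**5. Shift in the mean (also assumed).** If k of 30 subjects are excluded and differ from the rest by d, the mean of all 30 differs from the reported mean by (k/30) × d. For k = 3 and d = 0.1 to 0.4 mm this is 0.010 to 0.040 mm, or 14% to 55% of 0.073 mm. The upper end needs both 3 exclusions in one group and a difference of twice the planned SD.

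**6. What a rescue rule would need.** The windows allow a reference-to-2-year interval of 640 − 56 = 584 to 820 − 28 = 792 days. A reference on days 57–59 gives 640 − 59 = 581 to 820 − 57 = 763 days, at most 3 days outside that range, so timing is no obstacle there. The 2-year side is different because the documents give no outer limit. For illustration, accepting exams up to day 865 lengthens the longest interval to 865 − 28 = 837 days (+5.7%). It would admit an exam 865 − 730 = 135 days from the midpoint, while day 639, 730 − 639 = 91 days from it, stays out unless an early limit is set as well.

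**The case for a change.** The strongest case for acting is that the remedy is cheap. The images are already taken, one flagged table would use them, and the primary result would not move. SAP 6.2 counts dated and scorable records in each interval but does not separate a missing image from one excluded by its date, and counts cannot show whether the excluded values differ. Apart from pre-operative and intra-operative withdrawals and COVID-related misses of the 6-week visit, subjects who discontinue are not replaced (Protocol 8.2). If someone later looks at the late exams post hoc, the cut-off will be chosen with the data in view.

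The factual part of this stands: such exams enter no primary or secondary summary, and a lost reference removes a subject from four time points. The case for a mandatory addition does not. Subjects who miss the 6-week visit because of COVID-19 can be replaced, precisely because that visit is the baseline (Protocol 6.4). The deviation listing already makes out-of-window visits visible by subject. Protocol 6.6 is triggered by an unscheduled visit and does not clearly cover a scheduled 2-year visit that runs late, so the conflict between requiring an exam and not using it is narrower than it looks. A rule for late exams alone would treat early and late departures unequally, and a symmetric one would rest on limits chosen without support in the documents. The recovered subjects would also be a selected group, since they attended off schedule.

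**Conclusion.** No change is needed. This is a fair trade-off: uniform timing of a time-dependent measurement is bought at the price of possibly discarding a few exams. The rule is stated in advance and matches the endpoint sections of both documents. The study is descriptive, with no decision hanging on the interval, and forgoing sensitivity analyses is an explicit choice in SAP 6.13. On assumed losses of 1 to 3 subjects per group the margin widens by 0.0013 to 0.0040 mm. A noticeable shift in the mean would require several exclusions in one group with clearly different migration, and nothing in the documents points to that. The true frequency is unknown and may be nil.

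The label points do not alter this. No other post-operative window exists for RSA exams, and SAP 2 applies Table 3 to the primary and secondary endpoints, so an analyst would use it despite its title. The Per Protocol wording cannot change the primary RSA result, because SAP 6.6 separately requires both 6-week and 2-year data.

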### 9.4 Interval Windows

Data collected throughout the study will be assessed for compliance with the protocol-specified visit schedule. **Error! Reference source not found.** Six windows are defined based on the number of days prior to or after surgery, Day 0. Visits conducted within the intervals shown in Table 9-1 will be assessed for compliance with the protocol. If multiple visits fall into the pre-operative window, or into the 6 Week post-operative window, the result collected most proximate to surgery will be utilized. If multiple measurements fall into the 3 Month, 6 Month, 1 Year, or 2 Year window, the last value (furthest from surgery) will be utilized for the analysis. All safety data will be included in the Safety analysis.

Table 9-1 Study Visit Interval Windows per Time and Events Table

Study Visit	Study Interval Window (days)
Pre-Op	-90 to DOS*
Operative	0
Prior to Discharge	Day 1 to Discharge
6 Weeks	28 to 56
3 Months	60 to 120

6 Months	135 to 225
1 Year	275 to 455
2 Years	640 to 820

\* For radiographs Pre-Op study film window is from -270 days to DOS.

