### 6.7.4 Harris Hip Score at Pre-Op, 6 weeks, 3 months, 6 months, 1 year, and 2 years

Harris hip scores are assessed at the Pre-Op visit and at 6 weeks, 3 months, 6 months, 1 year and 2 years. Results within each visit window will be summarized and changes from baseline will be provided using the Per Protocol Analysis Set. Standard continuous summaries will be supplemented with 95% confidence intervals.

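### In the 3-month to 2-year windows, scores repeated at a later unscheduled hip visit replace the scheduled-visit scores, and only in subjects who needed extra care for the hip

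*SAP*

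**What the plan says.** **Selection rule.** SAP section 2 provides that, for every visit later than discharge, "if multiple measurements fall into the window then the last value within the window will be utilized for analysis". Protocol 9.4 has the same rule for the 3-month, 6-month, 1-year and 2-year windows: "the last value (furthest from surgery) will be utilized for the analysis". For the 6-week window the two differ. Protocol 9.4 takes the value nearest to surgery, while the SAP rule takes the last one.

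**What is eligible.** SAP section 2 selects by day, not by visit label: "Only data which can be attributed to the visit intervals in Table 3 will be used in the analysis of primary and secondary endpoints". It then separates the two labels: "This visit will be hereafter referred to as the Analysis Visit and the originally recorded visit as the Nominal Visit". Neither document gives the scheduled visit precedence or sets unscheduled results aside.

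**Where second values come from.** Protocol 6.6 applies "If a subject requires an additional visit during a study interval for their study hip" and the subject is seen by delegated study staff; "then the following information shall be repeated". The list that follows is Harris Hip, Hip Evaluation, HOOS Jr., FJS-12 and adverse events. It contains no radiographs and no RSA exam.

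**How the selected value is used.** For Harris Hip (SAP 6.7.4), and in the same terms for HOOS Jr. and FJS-12: "Results within each visit window will be summarized and changes from baseline will be provided using the Per Protocol Analysis Set". Hip Evaluation is summarised as categorical data by visit (SAP 6.7.7). The FJS-12 baseline is the 6-week value (SAP 6.1). SAP 6.13 plans no sensitivity analyses.

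**The concern.** Most subjects will have one value per window, so the last-value rule will not affect them. It matters for subjects who come back within the window because the study hip needed attention. For them, a later repeat displaces the routine score. Whether a scheduled score is kept therefore depends on a hip-related event after it was taken, and that event is probably related to the score itself.

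The study is descriptive, so its product is the set of visit-specific summaries by approach and overall. Harris Hip, HOOS Jr. and FJS-12 all run from 0 to 100 with higher being better (SAP Appendix A). If return visits mostly record problems, the summaries shift toward worse scores, and Hip Evaluation shifts toward less favourable categories. No planned analysis would show how much.

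A smaller consequence concerns the optional correlation of scores with RSA observations (SAP 6.8). The in-interval repeat has no RSA exam, so an unscheduled score could be paired with an RSA exam from a different day in the window.

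**Working it through.** **Plan's own figure.** The documents give no precision or expected value for these scores. Their only design figure is the margin of error for 2-year subsidence, 2 × 0.2/√30 = 0.073 mm (Protocol 9.8, SAP section 5). It reproduces, and this point does not touch it.

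**Step 1: when replacement occurs.** Take a subject seen on schedule at Day 365 and again, unscheduled, at Day 430. Both days lie in the 1-year window (275 to 455). Protocol 6.6 requires the four instruments at Day 430, SAP section 2 attributes both sets to 1 year, and the last is kept, so the Day 365 scores drop out. If the unscheduled visit comes before the scheduled one, the scheduled value is kept. If it falls outside every window, it is not used.

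**Step 2: days on which replacement can occur.** The inputs are the maximum and midpoint days in SAP Table 3. I assume that scheduled visits fall on the midpoint.

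| Window | Maximum − midpoint | Days |
|---|---|---|
| 3 months | 120 − 90 | 30 |
| 6 months | 225 − 180 | 45 |
| 1 year | 455 − 365 | 90 |
| 2 years | 820 − 730 | 90 |
| Total | | 255 |

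Day 28 to Day 820 is 820 − 28 + 1 = 793 days, and 255/793 = 32%.

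**Step 3: size of a shift.** If k of n subjects have a replaced score that is d points lower, the group mean changes by −k × d/n. With n = 30 per approach (Protocol 9.2), and k and d assumed because the documents give neither:

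| Replaced subjects (k) | d = 10 | d = 20 | d = 30 |
|---|---|---|---|
| 1 of 30 | −0.3 | −0.7 | −1.0 |
| 3 of 30 | −1.0 | −2.0 | −3.0 |

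Deficits of this order are possible on the SAP's scoring tables. Harris pain moving from None to Moderate is 44 − 20 = 24 points. HOOS Jr. moving from raw 2 to raw 8 is 85.257 − 64.664 = 20.6 points.

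**Step 4: dependence on direction.** Let q be the share of replaced scores that are worse by d, the rest being better by d. The shift is −(k/n) × d × (2q − 1). With k/n = 10% and d = 20:

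- q = 1: −2.0
- q = 0.75: −1.0
- q = 0.5: 0
- q = 0.25: +1.0

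**Step 5: FJS-12 change from baseline.** Under the SAP rule the 6-week window is exposed too. A worse unscheduled score there lowers the baseline and raises the mean change by k × d/n, against the effect in Step 3. Under Protocol 9.4 the 6-week value nearest to surgery is kept, so a later repeat does not displace it.

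**The case against.** The strongest reply is that the rule is prespecified, that both documents agree on it for the 3-month to 2-year windows, and that the plan itself defines 1 year as Day 275 to 455. A score from Day 430 is a valid 1-year value on those terms. A reader might infer that the replaced scores no longer describe the nominal time point. The documents do not support that, because a scheduled visit on Day 430 would also be accepted. What remains is the manner of selection: a second value exists only where the hip needed an extra visit.

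A reader might also infer that the bias is always downward. Protocol 6.6 says only that the subject requires another visit for the hip, not that the hip is doing badly. Protocol 7.3 and 7.4 ask for adverse events to be followed to resolution or stability, so some return visits may record recovery. Step 4 shows the shift vanishing when half the replaced scores are worse. For FJS-12 change, the SAP's 6-week rule can act in the opposite direction. This objection stands: the direction is likely, not established.

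A third tempting reading takes all days covered by the 6-week to 2-year windows as the exposure: 29 + 61 + 91 + 181 + 181 = 543 of 793, or 68%. That overstates it. The sum includes the 6-week window, where the documents conflict, and the days before the scheduled visit, when the scheduled value is kept.

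Finally, the consequences are limited. There are no hypotheses, and the confidence intervals are labelled exploratory. Hip Evaluation is a secondary endpoint only in the SAP, and the correlation analysis is optional. All of that stands and bears on priority, not on whether the rule selects as described.

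**Conclusion.** The point holds for the 3-month to 2-year windows. A result from an unscheduled hip visit after the scheduled visit in the same window replaces the scheduled result for Harris Hip, Hip Evaluation, HOOS Jr. and FJS-12, and only in subjects who needed extra care for the hip. The likely effect is a shift toward worse scores or less favourable categories, which later recovery visits could offset.

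The size cannot be derived from the documents. The range of 0.3 to 3.0 points in an approach-group mean rests on the assumption of 1 to 3 replaced subjects in 30, each scoring 10 to 30 points lower. The 32% of follow-up days on which replacement can occur rests on scheduled visits falling at the midpoint.

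The 6-week window needs separate mention. The SAP rule exposes the FJS-12 baseline and would push FJS-12 change upward. Protocol 9.4 states a different rule, so the two must be reconciled.

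The primary RSA endpoint is essentially unaffected, because the in-interval repeat list has no RSA exam. The affected endpoints are secondary and descriptive. The change is still worth making before database lock, since it is nearly free and no planned analysis would reveal the effect.

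**What to change.** In SAP section 2 and Protocol 9.4, use one rule for the 6-week, 3-month, 6-month, 1-year and 2-year windows:

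- Analyse the scheduled (nominal) visit result if it is in window.
- If there is none, analyse the in-window result closest to the Midpoint Day. SAP Table 3 already gives that day for each of these five windows, although no current rule uses it. Pre-Op and Prior to Discharge have no midpoint and are not part of this change.
- List unscheduled-visit results separately.

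This removes the replacement wherever a scheduled in-window result exists, and it settles the 6-week conflict between the two documents. The cost is a short text change in the SAP and a matching protocol clarification, with no new data. The small downside is that deterioration seen at a later unscheduled visit would appear in the listings and adverse event data rather than in the visit summary.

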### **3 Levels of Significance**

There are no specific hypotheses being tested in this study. To facilitate clinical interpretation, confidence intervals will accompany primary and secondary endpoint estimates and will be 2-sided 95% confidence intervals; these confidence intervals are considered to be exploratory.

### **4 Analysis Sets**

The following analysis sets are defined:

- **All Enrolled** – Subjects will be considered enrolled if they have consented and authorized release of their personal health information.
- **Safety** – The Safety Analysis Set consists of all enrolled subjects who receive THA surgery. Subjects will be analyzed according to the surgical approach applied during of the study.
- **Per Protocol** – The Per Protocol (PP) Analysis Set will be a subset of Safety Set subjects who have no major inclusion/exclusion protocol violations, and who have a 6 weeks RSA exam and at least one post-baseline RSA exam. Subjects will be analyzed according to the actual treatment (surgical approach) received during of the study.

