### **6.4 6 Weeks (Day 28-56)**

All subjects will undergo a model-based RSA examination. For all sites, the 6-week exam will be used as the reference examination. RSA radiographs will be obtained with subjects in a supine position. A duplicate RSA exam will be conducted at this time-point to calculate the intra-subject measurement error.

Additionally, the subject will have the following health and functional status evaluations:

- Harris Hip Score; ROM optional
- Hip Evaluation
- HOOS Jr.
- Forgotten Joint Score
- Adverse Events (if applicable)
- Radiographs
  - AP Femur
  - Lateral

The information collected from the '6 Week' visit will be populated on the appropriate eCRFs as indicated in the Time and Events Table (Section 1.1).

NOTE: Any subject that is unable to complete their 6 week visit due to the COVID-19 Pandemic can be replaced; as many endpoints use this timepoint as the baseline value. Subjects unable to complete their 6 week visit will not be withdrawn because of this missing visit but continue to be followed according to the protocol.

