### **8.2    Subject Early Discontinuation**

Every subject should be encouraged to remain in the study until they have completed the protocol-required 2-year follow-up period. If the subject discontinues prematurely from the study, the reason for discontinuation must be documented in the source documents and site files and submitted via eCRF.

Data which have been received on subjects who discontinue prematurely will be included in the analysis of results. Subjects who discontinue prematurely, excluding those withdrawn pre-operatively, intra-operatively or those subjects who were unable to complete their 6 week visit due to the COVID-19 Pandemic, will not be replaced.

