### Per Protocol (PP) Analysis Set

The Per Protocol (PP) Analysis Set will be a subset of Safety Set subjects who have no major inclusion/exclusion protocol violations, and who have a baseline RSA exam and at least one post-baseline RSA exam. Subjects will be analyzed according to the actual treatment (surgical approach) received during of the study.

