### 6.7.6 Forgotten Joint Score (FJS-12) at 6 weeks, 3 months, 6 months, 1 year and 2 years

FJS-12 scores are assessed at 6 weeks, 3 months, 6 months, 1 year and 2 years. Results within each visit window will be summarized and changes from baseline will be provided

using the Per Protocol Analysis Set. Standard continuous summaries will be supplemented with 95% confidence intervals.

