#### 6.7.7 Hip Evaluation at Pre-Op, 6 weeks, 3 months, 6 months, 1 year and 2 years

Hip evaluation questions will be summarized at Pre-Op, 6 weeks, 3 months, 6 months, 1 year and 2 years as categorical data using the Per Protocol Analysis Set. The first two questions (“How satisfied are you with this procedure?” and “Would you have this procedure again?”) will not be summarized at the Pre-Op visit.

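### Harris Hip, HOOS Jr., FJS-12 and Hip Evaluation are summarised only in subjects who have a 6-week and a later RSA exam, a condition these instruments do not need

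*SAP*

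**What the plan says.** **Who is in the set.** SAP 4 defines the Per Protocol set as Safety Set subjects without major inclusion/exclusion violations "who have a 6 weeks RSA exam and at least one post-baseline RSA exam". Protocol 9.5 has the same condition, worded as subjects "who have a baseline RSA exam and at least one post-baseline RSA exam". The Safety Set has no RSA condition: "The Safety Analysis Set consists of all enrolled subjects who receive THA surgery".

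**Which endpoints use it.** For Harris Hip (SAP 6.7.4): "Results within each visit window will be summarized and changes from baseline will be provided using the Per Protocol Analysis Set". SAP 6.7.5 says the same for HOOS Jr. FJS-12 (SAP 6.7.6) is reported "using the Per Protocol Analysis Set. Standard continuous summaries will be supplemented with 95% confidence intervals", and Hip Evaluation (SAP 6.7.7) "as categorical data using the Per Protocol Analysis Set". Protocol 9.12.2 also names only this set for the three scores. In contrast, RSA translation endpoints are planned on both the Per Protocol and the Safety Set (SAP 6.6 and 6.7.1; Protocol 9.12.1 and 9.12.2). SAP 6.13 plans no sensitivity analyses.

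**Who keeps being followed.** Protocol 6.4 allows replacement of subjects who miss the 6-week visit because of COVID-19, but keeps them in the study: "Subjects unable to complete their 6 week visit will not be withdrawn because of this missing visit but continue to be followed". Protocol 6.5 collects all four instruments at 3 months, 6 months, 1 year and 2 years. On early leavers, Protocol 8.2 states: "Data which have been received on subjects who discontinue prematurely will be included in the analysis of results".

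**The concern.** Functional and health status is a secondary objective in its own right (Protocol 3.2; SAP 1.1.2), but it is answered on a subset selected by whether RSA exams took place. SAP 6.1 sets a pre-operative baseline for Harris Hip and HOOS Jr., so change at any later visit needs neither the 6-week visit nor an RSA exam. A subject with valid pre-operative and 2-year scores but no 6-week RSA exam is left out for a reason unrelated to the endpoint.

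Two groups are affected: subjects who missed 6 weeks because of COVID-19, and subjects who attended 6 weeks but left before any later RSA exam. At stake are the precision of the functional summaries and how well they represent the treated subjects.

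**Working it through.** **1. The plan's own precision figure.** SAP 5 and Protocol 9.8 give 2 × SD/√n = 2 × 0.2/√30 = 0.073 mm. This reproduces. It concerns 2-year subsidence only, and this point does not depend on it. The documents give no SD for the functional scores, so the effect below is a relative interval width.

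**2. What each requirement does to each instrument.**

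| Instrument | Baseline (SAP 6.1) | Needs an RSA exam? | Subject with no 6-week visit: what could be summarised | What the plan summarises |
|---|---|---|---|---|
| Harris Hip | Pre-operative | No | Later visits and change | Nothing post-operative |
| HOOS Jr. | Pre-operative | No | Later visits and change | Nothing post-operative |
| FJS-12 | 6 weeks (questionnaire) | No | Later visits; change not available | Nothing |
| Hip Evaluation | By-visit categories | No | Later visits | Nothing post-operative |

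**3. COVID-19 group: size.** The number is not in the documents. Assume 5 to 15 such subjects in addition to 90 subjects who meet the Per Protocol definition, all with scorable data and the same SD.

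- Share of followed subjects left out: 5/95 = 5.3%; 15/105 = 14.3%.
- Half-width is proportional to 1/√n (ignoring the small change in the t quantile). Narrowing of the pooled interval if they are included: 1 − √(90/95) = 2.7%; 1 − √(90/105) = 7.4%.

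**4. Early-leaver group: which summary is affected.** The 6-week window is days 28 to 56 and the 3-month window opens at day 60 (SAP 2). A subject who leaves before day 28 has no 6-week score to lose. One who attends 6 weeks and leaves before a later RSA exam has, in essence, only 6-week post-operative scores, so those are what the plan drops. For Harris Hip even that score may be missing: range of motion is optional at 6 weeks (Protocol 9.12.2), and SAP 8.1 voids the total if an item is unanswered. The documents give neither a number of such subjects nor a score difference, so no size can be calculated.

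**5. Where these subjects do appear.** Protocol 9.11 summarises baseline Harris Hip and HOOS Jr. on the Safety Set as well, and SAP 6.2 counts dated and scorable records of the three scores on the Safety Set. Neither is an outcome summary.

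**The case against.** The best defence is that this is an RSA study and one cohort for migration and function is coherent: the functional description then belongs to the subjects whose migration is reported. That stands for the exploratory correlations in SAP 6.8, which need both. It does not justify making that cohort the only one for a separate secondary objective.

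It also stands that the endpoints are descriptive, no hypothesis is tested, the intervals are labelled exploratory (SAP 3), and the sample size was set only for subsidence.

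Some subjects may be rescued. Protocol 6.6 provides for an RSA exam at an unscheduled visit if the in-window one was missed. Whether it could serve as the 6-week exam is unclear, because SAP 2 admits only in-window data for primary and secondary endpoints.

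A reader might infer more than the documents support:

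- **That the restriction flatters the device.** Missing a visit because of COVID-19 has no stated link to hip function, so that group shows a loss of precision and no demonstrated bias. Only early leavers could produce such an effect, essentially at 6 weeks, by an unknown amount.
- **That the scores appear nowhere.** Baseline scores and record counts do appear on the Safety Set. The difference between the SAP 6.2 counts and the endpoint tables is not a defect, since they serve different purposes.
- **That Protocol 8.2 is contradicted.** It is a general statement and can be read as inclusion wherever a subject qualifies; leavers do enter the Safety Set analyses. The exclusion sits poorly with it, but is not a clear contradiction.
- **That unreadable RSA images enlarge the loss.** The set requires an exam, not a readable one, so on a plain reading those subjects stay in.

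**Conclusion.** The point holds as a loss of valid functional data from the outcome summaries, with a cost mainly in precision and representativeness. For the COVID-19 group the pooled interval would be about 3% to 7% narrower with them included. That rests on an assumed 5 to 15 subjects beyond 90, complete scores and a common SD. For early leavers the effect is confined essentially to the 6-week summary and cannot be sized. FJS-12 change from baseline is lost for anyone without a 6-week questionnaire under any analysis set, so that part is not attributable to the RSA condition. No test or primary result is affected. The change is still worth making, because following the plan as written leaves out data that the protocol deliberately goes on collecting.

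**What to change.** In SAP 6.7.4 to 6.7.7, and in Protocol 9.12.2 for the three scores, remove the RSA-exam condition for these four instruments. Summarise each on Safety Set subjects who have the score at that visit, plus the instrument's own baseline score where change is reported. Either of two forms would do:

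- **Main analysis:** Safety Set subjects without major inclusion/exclusion violations, with the current Per Protocol version kept alongside. This keeps the eligibility restriction but adds a population that SAP 4 must define.
- **Supportive table at least:** the Safety Set as already defined, next to the Per Protocol table, as already planned for the RSA endpoints.

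State in SAP 6.7.6 that FJS-12 change is not available without a 6-week questionnaire, while by-visit FJS-12 results are. Leave the RSA endpoints unchanged.

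The cost is a small wording change in the SAP and protocol and one extra run of existing tables. The protocol edit is an amendment; whether it needs REB approval depends on whether it counts as substantial under Protocol 12.2. The functional and RSA tables will have different n, which a footnote can explain.
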